3.1.3.2 Survival/Long-term/Response Follow-up

After completion of the Clinical/Safety Follow-up period, all subjects will then enter the Survival/Long-term Follow-up period. During this period, clinic visits or telephone contact every 3 months will be performed to assess survival status. The duration of the Survival/Long-term Follow-up period will be approximately 2 years following the first dose of study drug, and a minimum of 12 months following the last dose of study drug.

After completion of the Safety Follow-up period, subjects who discontinue study with ongoing SD, PR, or CR at the EOT visit will enter the Response Follow-up period. This period will occur simultaneously with the Survival Follow-up period for these subjects. These subjects will continue to have radiological and clinical tumor assessments every 3 months (12 weeks) during the Response Follow-up period or until disease progression or withdrawal of study. Radiological tumor assessments for subjects who have ongoing clinical benefit may continue to be collected after subjects complete the survival phase of the study.

Subjects in the Survival/Long-term Follow-up period who have progression of disease will be allowed to receive tumor-directed therapy as required.

[figure not shown]
Data from imaging assessments for subjects who have ongoing clinical benefit may continue to be collected after subjects complete the survival phase of the study.

3.1.4 *Re-treatment during Safety/Survival/Long-term Follow-up*

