Re-treatment may be allowed in this study with disease progression during follow-up. Subjects completing approximately 48 weeks of study treatment or who discontinue therapy due to a CR, who enter Safety/Survival/Long-term Follow-up with ongoing disease control (CR, PR, or SD) for reasons other than drug-related toxicity, may be eligible for re-treatment upon subsequent confirmed disease progression within 12 months of the last dose of study drug, on a case-by-case basis, after careful evaluation and discussion with the BMS Medical Monitor to determine whether the benefit/risk ratio supports administration of further study drug. Subjects meeting criteria for re-treatment will be treated for a maximum duration of 2 years from first dose of nivolumab, with the originally assigned dose regimen (eg, same dose and dose schedule administered during the initial treatment period) or modified dose regimen, unless that dose and schedule were subsequently found to exceed the MTD, in which case the subject will be treated at the next lower or alternate dose and schedule (see [Table 4.5.3-1](#)). Subjects entering this phase will follow the same Time and Events schedule as outlined in [Section 5](#). Samples for PK will be collected less frequently. During re-treatment, pharmacodynamic biomarker samples obtained from blood will be collected as outlined in [Section 5.7](#).

The treatment and follow-up schematic for Parts 1, 2, and 3, and the pharmacology substudy is presented in [Figure 3.1.4-1](#). The study design schematic for the clinical pharmacology substudy is presented in [Figure 3.1.4-2](#).

[figure not shown]
Figure 3.1.4-1: Treatment and Follow-Up Schematic for CA017003--All Study Parts

Note: For Part 3 bladder cohort, Additional Treatment will not include ipilimumab

Abbreviations: CR = complete response; EOT= end of treatment; PD = progressive disease; PI = principal investigator; PR= partial response; SD = stable disease.

Figure 3.1.4-2: Study Schematic of Clinical Pharmacology QTc Substudy

*: Baseline ECGs should be collected prior to the start of Cycle 0 (Day -1 preferred, up to 5 days prior to Cycle 0 is allowed).

Abbreviations: ECG = electrocardiogram; Q4W = every 4 weeks; QD = once daily.

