A subset of subjects with solid tumors treated with immunotherapy may derive clinical benefit despite initial evidence of PD. Subjects will be permitted to continue on treatment beyond initial RECIST v1.1 (see [Appendix 3](#)) or IWG-defined PD, as long as they meet the following criteria:

- Investigator-assessed clinical benefit and not having rapid disease progression;
- Continue to meet all other study protocol eligibility criteria;
- Tolerance of study drug;
- Stable performance status;
- Treatment beyond progression will not delay an imminent intervention to prevent serious complications of disease progression (eg, CNS metastases);
- Subject provides written informed consent prior to receiving any additional nivolumab, ipilimumab, or BMS-986205 treatment using an ICF describing any reasonably foreseeable risks, discomforts, or other alternative treatment options.

The assessment of clinical benefit should take into account whether the subject is clinically deteriorating and unlikely to receive further benefit from continued treatment. All decisions to continue treatment beyond initial progression must be documented in the study records. Subjects will be re-consented to explain the rationale for this ongoing treatment.

3.5.2 *Discontinuation Due to Further Progression (Confirmed Progression)*

Subjects should discontinue study drug upon further evidence of further progression, defined as an additional 10% or greater increase in tumor burden volume from time of initial progression (including all target lesions and new measurable lesions).

The tumor burden volume from time of initial progression should be used as the reference baseline for comparison with the postprogression assessment.

Any new lesion considered nonmeasurable at the time of initial progression may become measurable and therefore must be included in the tumor burden measurement as follows:

For solid tumors: New lesions are considered measurable at the time of initial progression if the longest diameter is at least 10 mm (except for pathological lymph nodes, which must have a short axis of at least 15 mm).

For statistical analyses that include the investigator-assessed progression date, subjects who continue treatment beyond initial investigator-assessed, RECIST v1.1 or IWG-defined progression will be considered to have investigator-assessed PD at the time of the initial progression event.

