3.5.3 Assessment Schedule for Subjects with Postprogression Treatment

Subjects should continue to receive monitoring according to the On-Treatment Assessments in [Section 5.4](#). Radiographic assessment by computed tomography (CT; preferred) or magnetic resonance imaging (MRI) described in [Section 5](#) is required when subjects continue postprogression treatment. For subjects who discontinue postprogression treatment with study drug, no additional radiographic assessments will be required.

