The anti-tumor activity of the expansion cohorts will be continuously monitored in all subjects who are evaluable for response using the measurements described in [Section 8.3.1](#). In the NSCLC cohort, 16 of 25 responses for the treatment naïve subjects would result in 80% CIs for an ORR that is strictly higher than the historical rate of 45.3%.⁶⁰ In the melanoma cohort, 22 of 35 responses for the treatment naïve subjects would result in 80% CIs for ORRs that are strictly higher than the historical rates of 58.0%.²⁸ In the bladder cohort, 16 of 30 responses would result in 80% CI for ORR that is strictly higher than the historical rate of 38.5%.⁶¹ The CIs are calculated using the Clopper-Pearson method.

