8.3 Endpoints

8.3.1 Primary Endpoint(s)

- The primary objective of this study is to establish safety, tolerability, and the MTD/MAD/alternate dose. The assessment of safety will be based on the incidence of AEs, SAEs, AEs leading to discontinuation, and deaths. In addition, clinical laboratory test abnormalities will be examined. AEs and laboratory values will be graded according to the NCI CTCAE v4.03.
- The co-primary objective, anti-tumor activity of BMS-986205 in combination with nivolumab in Part 2 (dose expansion) and BMS-986205 in combination with both nivolumab and ipilimumab in Part 3, will be measured by ORR, DoR, and PFSR based on RECIST v1.1 for solid tumors or IWG for blood tumor. For Parts 1 and 2, disease assessment with CT and/or MRI as appropriate will be performed at baseline, end of Cycle 2, and every 8 weeks. For Part 3, in the melanoma cohorts, the first tumor assessment will occur at Week 12 (\pm 1 week); subsequent imaging will be every 8 weeks thereafter during the treatment period; for NSCLC, imaging assessments will occur every 6 weeks during the treatment period; for bladder, imaging assessments will occur every 6 weeks during the treatment period up to 24 weeks, and then occur every 12 weeks thereafter during the treatment period. For all study parts, assessments continue every 12 weeks for the first year after the EOT visit, and then every 6 months thereafter, up to 2 years following the EOT visit until disease progression per RECIST v1.1 or IWG, or until confirmed disease progression for subjects treated beyond progression (defined as an additional 10% or greater increase in tumor burden volume from time of initial progression including all target lesions and new measurable lesions), at the completion of follow-up, or until subjects withdraw from the study.
- Best overall response (BOR) is defined as the best response designation over the study as a whole, recorded between the dates of first dose until the last tumor assessment prior to subsequent therapy. CR or PR determinations included in the BOR assessment must be confirmed by a second scan performed no less than 4 weeks after the criteria for response are first met. For those subjects who have surgical resection, only presurgical tumor assessments will be considered in the determination of BOR.
- ORR is defined as the proportion of all treated subjects whose BOR is either a CR or PR.

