- DoR, computed for all treated subjects with a BOR of CR or PR, is defined as the time between the date of first response and the date of disease progression or death, whichever occurs first.
- PFSR at 24 weeks, 1 year, and 2 years: The proportion of treated subjects remaining progression free and surviving at 24 weeks, 1 year, and 2 years if sufficient data are available. The proportion will be calculated by the Kaplan-Meier estimate, which takes into account censored data.

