4.2 Best Overall Response: All Time Points

The best overall response is determined once all the data for the subject are known. It is the best response recorded from the start of the study treatment until objectively documented progression per RECIST Criteria or subsequent cancer therapy, whichever happens first taking into account any requirement for confirmation. The subject's best overall response assignment will depend on the findings of both target and non-target disease and will also take into consideration the appearance of new lesions.

Best response is defined as the best response across all time points with subsequent confirmation. CR or PR may be claimed only if the criteria for each are met at a subsequent time point as specified in the protocol (generally 4 weeks later).

In this circumstance, the best overall response can be interpreted as specified in Table 4.2-1. When SD is believed to be the best response, it must meet the protocol-specified minimum time from baseline. Measurements must have met the SD criteria at least once after study entry at a minimum interval (in general not less than 6–8 weeks) that is defined in the study protocol.

Table 4.2-1: Best Overall Response When Confirmation of CR and PR is Required

Overall Response	Overall Response	BEST Overall Response
First Time Point	Subsequent Time Point	
CR	CR	CR
CR	PR	SD, PD or PR ^a
CR	SD	SD provided minimum criteria for SD duration met, otherwise, PD
CR	PD	SD provided minimum criteria for SD duration met, otherwise, PD
CR	NE	SD provided minimum criteria for SD duration met, otherwise NE
PR	CR	PR
PR	PR	PR
PR	SD	SD
PR	PD	SD provided minimum criteria for SD duration met, otherwise, PD
PR	NE	SD provided minimum criteria for SD duration met, otherwise NE
NE	NE	NE

CR = complete response, PR = partial response, SD = stable disease, PD = progressive disease, NE = not evaluable.

^a If a CR is truly met at first time point, then any disease seen at a subsequent time point, even disease meeting PR criteria relative to baseline, makes the disease PD at that point (since disease must have reappeared after CR). Best response would depend on whether minimum duration for SD was met. However, sometimes 'CR' may be claimed when subsequent scans suggest small lesions were likely still present and in fact the subject had PR, not CR at the first time point. Under these circumstances, the original CR should be changed to PR and the best response is PR.

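### Best overall response in Section 8.3.1 has no stop at progression and contradicts Appendix 3, so a first response after progression counts in the co-primary ORR and gets a negative duration

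*Combined protocol and SAP*

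**What the plan says.** Section 8.3.1 and the synopsis (Primary Endpoints) take BOR over the study as a whole, "recorded between the dates of first dose until the last tumor assessment prior to subsequent therapy". CR and PR must be confirmed at least 4 weeks later. ORR is the share of treated subjects whose BOR is CR or PR. DoR, for every such subject, "is defined as the time between the date of first response and the date of disease progression or death", whichever comes first.

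Appendix 3, Section 4.2, gives a different window for solid tumors: from the start of treatment "until objectively documented progression per RECIST Criteria or subsequent cancer therapy, whichever happens first".

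Other sections decide whether the difference matters:

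- Section 3.5.1 allows treatment beyond initial progression, and Section 3.5.3 says imaging "is required when subjects continue postprogression treatment".
- Section 3.5.2 says that, for analyses using the investigator-assessed progression date, such subjects "will be considered to have investigator-assessed PD at the time of the initial progression event".
- Section 3.1.4 allows some subjects in follow-up to be treated again: they "may be eligible for re-treatment upon subsequent confirmed disease progression within 12 months of the last dose of study drug".
- Appendix 3, Section 3.1, measures PR against the baseline sum of diameters.

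**The concern.** For solid tumors there are two BOR windows in force and no stated order of precedence. For DLBCL, the IWG text gives no BOR window, so Section 8.3.1 is the only rule and it has no stop at progression.

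If Section 8.3.1 is followed literally, a subject who progresses, stays on treatment and then has a first confirmed response is an ORR responder. The same subject has a progression date earlier than the response date, so the DoR formula returns a negative time. In the progression-free survival rate (PFSR), that subject has already progressed.

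ORR and DoR both measure the co-primary efficacy objective, and the protocol reads ORR against fixed historical rates. Compared with the Appendix 3 window, the Section 8.3.1 window can only leave ORR unchanged or raise it. Two analysts who both follow the protocol could report different ORRs.

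**Working it through.** **1. A dated example.** Part 2 scans fall at the end of Cycle 2 (Week 8) and every 8 weeks after that. Take a subject with initial progression at Week 8 who is treated beyond progression, first meets PR at Week 16, has it confirmed at Week 24, and receives no subsequent therapy.

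| Quantity | Section 8.3.1 window | Appendix 3 window |
|---|---|---|
| BOR | PR | PD |
| Counted in ORR | yes | no |
| DoR, with the Section 3.5.2 progression date | 8 - 16 = -8 weeks | not computed |
| PFSR | event at Week 8 | event at Week 8 |

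**2. Can it happen?** Yes, but the route is narrow. PR is judged against baseline, so target lesions can grow enough for progression and later fall 30% below baseline. If progression came from a new lesion that persists, Appendix 3, Table 4.1-1, keeps every later time point at PD. Section 3.5.2 ends treatment on a further 10% increase in tumor burden.

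Re-treatment is a smaller route. It is open only to subjects who entered follow-up in CR, PR or SD, so it can add only responders whose best response had been SD. It also applies only if renewed study drug is not subsequent therapy, a term Section 8.3.1 leaves undefined.

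**3. The plan's own figures.** For the 35-subject cohorts (historic ORR 10%, target 30%, at least 7 responses), exact binomial gives:

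- P(X >= 7 | n = 35, p = 0.30) = 0.935; stated 94%.
- P(X >= 7 | n = 35, p = 0.10) = 0.055; stated 6%.
- The 80% Clopper-Pearson lower limit for 7/35 is the 0.10 quantile of Beta(7, 29) = 11.5%; stated 11%.

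**4. What one responder changes.** The 80% Clopper-Pearson lower limit for k responses in n is the 0.10 quantile of Beta(k, n - k + 1). The protocol sets benchmarks of this kind in Sections 8.1.2 and 8.1.3; for bladder in Part 3, for instance, "16 of 30 responses would result in 80% CI for ORR that is strictly higher than the historical rate of 38.5"%.

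| Cohort | Historic ORR | One fewer | At benchmark |
|---|---|---|---|
| Part 2, n = 35 | 10% | 6/35: 9.3% | 7/35: 11.5% |
| Part 2, n = 27 | 25% | 10/27: 24.4% | 11/27: 27.7% |
| Part 2, n = 37 | 5% | 4/37: 4.8% | 5/37: 6.7% |
| Part 3 bladder, n = 30 | 38.5% | 15/30: 37.0% | 16/30: 40.2% |
| Part 3 NSCLC treatment-naive, n = 25 | 45.3% | 15/25: 45.2% | 16/25: 49.2% |

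In all five, the lower count misses the historical rate and the higher count clears it. The sixth benchmark, melanoma at 22/35, is left out: its lower limit is 50.6%, below its 58.0% rate.

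**5. Illustration only.** The documents give no rate of first response after progression. If such responses added 1, 2, 3 or 5 percentage points to a true 10% rate, P(X >= 7 | n = 35) would rise from 5.5% to 8.3%, 11.9%, 16.2% or 26.5%. The added points are assumptions, and these are not error rates of a binding test.

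**The case against.** The best reply is that the plan already points to Appendix 3. The synopsis (Efficacy Measure) and Section 5.4 refer to that appendix for RECIST, and Sections 8.3.1 and 8.4.2 base response on RECIST v1.1. Appendix 3, Section 4.3.1, also describes duration in a way that presupposes response before progression. On that reading, Section 8.3.1 is only an incomplete summary. This shows what the authors may have intended, but it does not settle the matter: Section 8.3.1 states its own, different window, nothing ranks the two, and the reply does not reach DLBCL.

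Other points stand as limits. In DLBCL there is no contradiction, only a missing stop, though the negative DoR can still arise. That PFSR counts the subject as progressed is not itself an error. Nothing shows that any subject will take this route.

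The benchmark table is also no evidence of frequency, since one subject matters at any integer cutoff. The planned ORR interval in Section 8.4.2 is 95%, not 80%. At 95% the lower limits at the five benchmark counts are 8.4%, 22.4%, 4.5%, 34.3% and 42.5%, all below their historical rates, so the extra responder changes none of those comparisons. The protocol tests no formal hypothesis and weighs the totality of efficacy data.

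**Conclusion.** The concern holds: the BOR rule is wrong as written and should be fixed. The conflict between Section 8.3.1 with the synopsis and Appendix 3 is plain in the text. The negative DoR follows directly from combining the Section 8.3.1 window with the Section 3.5.2 progression date.

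The effect on ORR is zero or upward, and its size cannot be derived from the documents. It is probably confined to few subjects, given how narrow the route is. One such subject would be enough to move any of the five 80% benchmarks, but no binding decision rests on them. The historical studies may have used either window; that cannot be checked here, so no claim is made about bias against them.

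**What to change.** In Section 8.3.1 and the synopsis, define BOR as the best response from first dose until the first of initial RECIST v1.1 or IWG progression or subsequent therapy. Then state that:

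- assessments before progression during additional treatment (Section 3.1.2) and Response Follow-up (Section 3.1.3.2) are included;
- the rule applies to DLBCL as well;
- responses after initial progression, including during re-treatment, do not count in ORR or DoR and are reported separately as descriptive results.

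The cost is a wording change in two places, with no new data. ORR may come out slightly lower, or unchanged if no subject responds first after progression. Negative durations can then no longer arise from this route.

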8.3.2 Secondary Endpoint(s)

8.3.2.1 Pharmacokinetics

For the first secondary objective (PK), selected BMS-986205 parameters, such as Cmax, Tmax, AUC(TAU), Ctrough, CLT/F, CLR/F, Vss/F, AI, %UR24, [REDACTED]

[REDACTED] from concentration-time

data during BMS-986205 monotherapy and concentrations at end of infusion and C_{trough} during combination treatment. Concentrations at end of infusion and C_{trough} for nivolumab and ipilimumab (where applicable) will be assessed during combination treatment (see [Section 5.5](#)).

8.3.2.2 *Pharmacodynamics*

The second secondary objective of pharmacodynamics, assessed by change from baseline for serum kynurenine and percent change from baseline, will be summarized.

8.3.2.3 *Efficacy*

The BOR, ORR, DoR, and PFS rates at pre-specified time points based on RECIST v1.1 and IWG will be the secondary efficacy endpoints for dose escalation and clinical pharmacology substudies.

8.3.2.4 *Immunogenicity*

The third secondary objective of immunogenicity will be assessed by the frequency of positive anti-drug antibody (ADA) to nivolumab or ipilimumab.

8.4 Analyses

8.4.1 *Demographics and Baseline Characteristics*

Frequency distributions of gender and race will be tabulated. Summary statistics for age, body weight, height, and body mass index will be tabulated.

8.4.2 *Efficacy Analyses*

Listing of tumor measurements will be provided by subject and study day in each arm and dose level. Individual subject's BOR will be listed based on RECIST v1.1 for solid tumors and IWG for blood tumor.

To describe the anti-tumor activity of BMS-986205 in combination with nivolumab and in combination with both nivolumab and ipilimumab, ORR will be calculated. ORR and corresponding 2-sided exact 95% CI by the Clopper and Pearson method will be provided by treatment, and/or dose level and tumor type (if appropriate). Median DoR and corresponding

2-sided 95% CI may be reported by treatment, and/or dose level and tumor type (if appropriate). DoR will be analyzed using the Kaplan-Meier method.

In addition, PFSR, the probability of a subject remaining progression free or surviving to 24 weeks, will be estimated by the Kaplan-Meier methodology, by treatment, tumor type and dose level. The corresponding 90% CI will be derived based on the Greenwood formula.

8.4.3 Safety Analyses

All recorded AEs will be listed and tabulated by system organ class, preferred term, treatment arm, and dose level and coded according to the most current version of MedDRA. Vital signs and clinical laboratory test results will be listed and summarized by treatment. Any significant PE findings and clinical laboratory results will be listed.

8.4.4 Pharmacokinetic Analyses

All individual PK parameters will be listed for each analytic including any exclusions and reasons for exclusion from summaries. Summary statistics will be tabulated for each PK parameter by treatment. Geometric means and coefficients of variation will be presented for Cmax, AUC(TAU), Ctrough, CLT/F, and CLR/F, after multiple-dose PK. Medians and ranges will be presented for Tmax. Means and standard deviations will be presented for all other PK parameters.

BMS-986205 dose dependency will be assessed in dose escalation lead-in. To describe the dependency on dose of BMS-986205, scatter plots of Cmax and AUC(TAU) versus dose may be provided for each day measured.

Urinary recovery data of BMS-986205 will be listed if available. Cumulative amount and cumulative percent recovered per interval will be summarized. Plots of individual cumulative percent of dose recovered in urine versus end of interval time will be provided. Mean plots of cumulative percent of dose recovered in urine versus end of interval time will also be provided.

